12.1 DEFINITION OF RESPONSE TO THERAPY

1. In the 16-week RW phase, response to therapy (as primary endpoint of efficacy) will be assessed by prevention of disease reactivations during the 16-week treatment in the RW phase
2. In the SAOL phase, response to therapy (as secondary endpoint of efficacy) will be assessed through the control of the active disease

For response to therapy, only the objective mAIDAI components will be evaluated as indicated below. Subjective mAIDAI components (see Appendix I) will not be considered to avoid any bias in the efficacy assessment in the open label part of the study. Justification for the revised response to therapy definitions is included in section 8.3.3.

o **Complete response**

No major end organ damage (=objective mAIDAI components)

- No fever (body temperature $\leq 100.4^{\circ}\text{F}/38^{\circ}\text{C}$)
- No diarrhea
- No transaminitis and/or hepatomegaly
- No splenomegaly and/or adenopathy
- No rash
- No uveitis
- No arthritis
- No radiologic CNS involvement
- No cytopenia ($\text{HgB} \geq 9.0$ and/or $\text{PLT} \geq 100$ and/or $\text{WBC} \geq 3.0$)

No systemic inflammation

- No hyperferritinemia (serum level $< 500 \text{ ng/mL}$)
- No increased CRP (serum level $< 2 \times \text{ULN}$)

Immunosuppressive therapies

- Discontinuation of systemic corticosteroids (excluding hydrocortisone for prevention of adrenal insufficiency) or other immunosuppressive therapies including biologics ongoing at baseline
- No start or dose increase of other immunosuppressive therapies including biologics

o **Partial response**

At least 50% reduction of the number of affected objective end organ damage categories at baseline and

- At least 50% of the systemic inflammatory markers (ferritin and/or CRP) increased at baseline reaching levels for complete response or
- Discontinuation of systemic corticosteroids (excluding hydrocortisone for prevention of adrenal insufficiency) or other immunosuppressive therapies including biologics ongoing at baseline

o **Disease Improvement**

A third response category of Disease Improvement is introduced to be utilized as a description of best response and in order to better describe initial treatment response to therapy and disease evolution over time. This is only used for analysis purposes and will not be evaluated for the decision whether to be eligible for the start of the RW phase. Disease Improvement is defined as:

- Reduction of the number of affected objective end organ damage categories at baseline by at least 1 or
- Normalization (i.e. reaching levels for complete response) or improvement ($> 50\%$ change from baseline for laboratory markers but still exceeding levels for complete response) of at least 50% of the systemic inflammatory markers affected at baseline
- Systemic corticosteroids (excluding hydrocortisone for prevention of adrenal insufficiency) or other immunosuppressive therapies including biologics must be at the same or lower doses compared to baseline

12.2 DEFINITION OF DISEASE REACTIVATION

For disease reactivation, only the objective mAIDAI components will be evaluated as indicated below. Subjective mAIDAI components (see Appendix I) will not be considered to avoid any bias in the assessment. Justification for the revised disease reactivation definitions is included in section 8.3.3.

During the RW-phase, the reference for a disease reactivation (for the primary endpoint assessment) will be the end of the SAOL phase (V8); for the SAOL phase, reference will be the previous visit, as patients enter the SAOL phase with an active disease.

- **Partial disease reactivation**

- Increase in the number of affected objective end organ damage categories by at least 2 or
- Increase in the number of affected objective end organ damage categories by at least 1 and worsening of at least 1 systemic inflammatory marker (i.e. serum ferritin levels ≥ 500 ng/mL or serum CRP $\geq 2x$ ULN) that was meeting complete response criteria before

- **Full disease reactivation**

- Increase in the number of affected objective end organ damage categories to at least the number of affected end organ damage categories at baseline (V1) and
- Exacerbation of at least 1 systemic inflammatory marker (i.e. serum ferritin levels ≥ 500 ng/mL or serum CRP $\geq 2x$ ULN) that was meeting complete response criteria before

Note: It is recommended that patients suffering from severe CNS manifestations are put on rescue immunosuppression treatment.

13 ASSESSMENT OF SAFETY

The Investigator will assess patient safety throughout the study. In addition, the DSMB, an independent committee, will analyze clinical or biological worsening of the status of study patients (i.e., SAEs) and also treatment failures and will assess the global safety of Tadekinig alfa (see details in Study Design section).

Safety assessment during the study will include:

- Prior to initiation of therapy, physical examination, vital signs, testing for active and life-threatening infections, complete blood count, clinical chemistry, coagulation and urinalysis.
- During treatment phase, physical examination, including ophthalmic examination, vital signs, routine laboratory (complete blood count, clinical chemistry, urinalysis), AEs, including AEs of Special Interest (AESI), concomitant medications, local tolerability index, immunogenicity, and coagulation tests.
- Regarding immunogenicity, ADAs assessment will be performed at Baseline V1, Week 2 (V3), Week 4 (V5), Week 12 (V7), Week 18 (V8), and RW Week 22 (V10), Week 26 (V11) and Week 34 (V13).
- Safety and disease activity labs will be assessed during hospitalization as required, weekly during visits for the first four weeks, then approximately monthly during visits until completion of the study, or at unscheduled visits.
 - weekly from Visit 0 to Visit 5;
 - monthly from Visit 6 to Visit 7;
 - at Visit 8 (6 weeks from Visit 7);
 - at Visit 9 (2 weeks from Visit 8);
 - at Visit 10 (2 weeks from Visit 9);
 - monthly from Visit 11 to Visit 13.

AEs will be collected from the time of informed consent through the end of the study. Definitions and reporting procedures for AEs and SAEs are provided in [Section 16. "Handling of Adverse Events".](#)

Details on routine safety laboratory assessments, virology, and serology tests, and collection of samples for ADAs (immunogenicity) are provided in [Table 2](#).

Physical examinations and vital signs (systolic and diastolic blood pressure, heart rate, respiratory rate, weight and body temperature) will be collected at all visits. Height is collected at Screening.

The Local Tolerability Index is provided in [Appendix 2](#).

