CMV = cytomegalovirus; CRP = C-reactive protein; EBV = Epstein-Barr Virus; ESR = erythrocyte sedimentation rate; FU = Follow up; HBV = hepatitis B virus; HCV = hepatitis C virus; HIV = Human Immunodeficiency Virus; ICF = Informed Consent Form; IL-18 = interleukin-18; IL-18 BP = interleukin-18 binding protein; mAIDAI = Modified Autoinflammatory Disease Activity Index; PK = pharmacokinetic; PT = prothrombin time; PTT = partial thromboplastin time; RW = Randomized Withdrawal phase; SAOL phase = Single arm open label phase; s.c. = subcutaneous; TB = tuberculosis

- a Reassessment of inclusion/exclusion criteria prior to treatment start
- b Investigational product (Tadekinig alfa or placebo) will be administered every 2 days \pm 5 hours to the patient. If the patient is located within close vicinity to the site, s/he has the option to go to the site for treatment administration or a Home Care Nurse may administer the treatment at the patient's residence. At V1 (Week 0), the first dose will be administered at the study center and the patient will remain at the site for a 2-hour observation.
- c Local Tolerability Index will be assessed by the Investigator or study nurse at the in-clinic visits including Week 0/Visit 1 when patient is at site under observation after first dose, and by the home care nurse on the subject's dose administration days, approximately every other day.
- d TB blood testing (QuantiFERON TB test) should be done at the local (hospital) lab or central lab, prior to treatment initiation
- e Additional sample for PK study will be collected at V1 and V5 prior to treatment and at 2 h, 4 h, 6 h and 24h post treatment (with a +/- 30 minutes window at each sample collection). Trough levels are calculated based on blood samples used for lab testing (no extra sample needed). Patients who are not hospitalized will need to present to the site 24h post-treatment for final PK sample collection, as well as AE and concomitant medication assessments.
- f If the patient has a disease reactivation during the tapering down, 28-day (4-week) SOC tapering cycles may be used and can be repeated during the 18-week SAOL study period.
- g A urine pregnancy test will be performed at each study visit on all females of childbearing potential. If the urine pregnancy test is positive, a serum pregnancy test will be performed.

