- h W18/Visit 8 will serve as the End of the SAOL period visit for those patients who discontinued treatment during the SAOL phase (an early termination form should be completed for these patients). These patients will not continue into the RW phase of the study.
- i Treatment of study drug administered to patients at W18/Visit 8 would be determined by randomization into RW phase. Final dose of treatment under the SAOL phase of the study will occur 2 days prior to W18/Visit 8. All W18 assessments must be performed prior to administration of study drug at W18/Visit 8.
- K Height collected at screening
- l Collection of Baseline lab samples may occur up to 3 days prior to the scheduled Week 0/Day 0 and Week 18/ Day 126 visit in order to have results available to confirm patient eligibility prior to study treatment.
- m Flow cytometry studies are necessary when a XIAP genetic abnormality has been found in the genetic testing. It is not required for patients with NLRC4 genetic mutations.

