14.2 Patient Recruitment - Screening Visit (before treatment start at V1)

- Review and signing of Child Assent and/or Informed Consent Form (ICF)
- Collection of AEs starts after signing ICF
- Demographics and medical history
- Completion of the Inclusion/exclusion checklist by the physician
- Physical examination with specific assessment of hepatosplenomegaly and vital signs (including height)
- Clinical evaluation by the physician using the mAIDAI (Appendix 1)
- Physician Global Assessment (PGA) (Appendix 3)
- Lab testing
 - Genetic evaluations

- Infection evaluations (CMV, EBV, etc.)
- Serology (HIV, HCV, HBV)
- Pregnancy test (UPT and/or hCG as applicable)
- Hematology, clinical chemistry, ESR (at local lab), urinalysis, CRP, Ferritin, TB blood testing (Note: QuantiFERON-TB testing should be done either at central lab or local [hospital] lab, prior to treatment initiation)
- Flow cytometry
- Coagulation (Thrombocytes, Fibrinogen, D-dimer, PTT, PT)
- Specialized lab testing
 - Serum: Total IL-18, free IL-18, IL-18BP

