17.6 Clinical Laboratory Abnormalities and Other Abnormal Assessments

Abnormal clinical laboratory findings that are judged by the Investigator as clinically significant must be recorded as AEs or SAEs if they meet the definition of an AE or an SAE, as defined in 16.2 and Section 16.3 respectively. Clinically significant abnormal laboratory findings or other abnormal assessments that are detected during the study or are present at Baseline and significantly worsen following the start of the study may be reported as AEs or SAEs.

The Investigator will exercise medical judgment in deciding whether abnormal laboratory values are clinically significant.

The grading of severity of AEs should take into account the reference values according to the ages of the subjects in the study.

The kidney function will be assessed by the calculation of the glomerular filtration rate using the Schwartz formula:

$GFR = KL/Pcr$ and it is expressed in ml/min per 1.73m² body surface area. L represents body length in centimeter, Pcr represent plasma creatinine concentration in mg per dl and K is a constant that varies as a function of age and sex, being 0.33 in preterm infants, 0.45 in full-term infants, 0.55 in children and adolescent girls and 0.70 in adolescent boys

Table 4: Grading of adverse events due to low levels of Creatinine Clearance or eGFR

Parameter	Grade 1 Mild	Grade 2 Moderate	Grade 3 Severe	Grade 4 Potentially Life-Threatening
Creatinine Clearance¹ or eGFR, Low Report only one	NA	< 90 to 60 ml/min or ml/min/1.73 m ² OR 10% to < 30% decrease from baseline	< 60 to 30 ml/min or ml/min/1.73 m ² OR ≥ 30% to < 50% decrease from baseline	< 30 ml/min or ml/min/1.73 m ² OR ≥ 50% decrease from baseline or dialysis needed

¹ Use the applicable formula (i.e., Cockcroft-Gault in mL/min or Schwartz in mL/min/1.73m²)

Low levels of Creatinine Clearance or eGFR reaching grades 3 and 4 will result in transient or permanent treatment discontinuation (see reference values in the Reference Study Manual)

Table 5: Grading of adverse events due to low levels of hemoglobin

Parameter	Grade 1 Mild	Grade 2 Moderate	Grade 3 Severe	Grade 4 Potentially Life-Threatening
Hemoglobin, Low (g/dL; mmol/L)¹				
≥ 18 years of age (both genders)	10.0 to <LLN 6.2 to <LLN	8.0 to <10.0 4.9 to <6.2	7.0 to <8.0 4.34 to <4.9	< 7.0 < 4.34
≥ 13 to <18 years of age (male only)	10.0 to 10.9 6.19 to 6.76	9.0 to < 10.0 5.57 to < 6.19	7.0 to < 9.0 4.34 to < 5.57	< 7.0 < 4.34

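### Height is scheduled only at screening, but eGFR is proportional to body length, so the schedule as written would understate eGFR in growing infants and young children

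*Protocol*

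**What the plan says.** Height appears in the protocol only at screening. The synopsis and Section 13 both say so ("Height is collected at Screening"), footnote K to Table 1 repeats it ("Height collected at screening"), and of the visit lists in Sections 14.2 to 14.9 only the screening list (14.2) names height. The repeated measurements include weight but not height: "Physical examinations and vital signs (systolic and diastolic blood pressure, heart rate, respiratory rate, weight and body temperature) will be collected at all visits".

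Section 17.6 assesses kidney function with the Schwartz formula, GFR = KL/Pcr, in which "L represents body length in centimeter". The K values begin at "0.33 in preterm infants, 0.45 in full-term infants", so very young patients are foreseen, and the eligibility criteria in Sections 10.2 and 10.3 set no minimum age.

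Table 4 grades a low eGFR either by its absolute value or by its percentage fall from baseline. The text below it reads: "Low levels of Creatinine Clearance or eGFR reaching grades 3 and 4 will result in transient or permanent treatment discontinuation". The synopsis, under the rules for stopping treatment in an individual, is weaker: grade 3 and 4 events *may* have this result.

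GFR is a listed safety endpoint (protocol Section 8.5.1). SAP Section 6.4.2 looks at its change from the SAOL baseline in the open-label phase and from the RW baseline in the randomised phase.

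**The concern.** The formula needs a length each time creatinine is measured. The schedule supplies one value, taken before V1, for 18 + 16 = 34 weeks of follow-up. In a growing child that value falls behind and eGFR falls with it, even when kidney function is unchanged. No length is scheduled at V8, which is the RW baseline for the safety analysis. Section 14.1 also lets screening be done by telemedicine on a local physician's examination, so the single length may not even be a study measurement.

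The protocol already allows for growth where study-drug dose is concerned: Section 11.2.1 updates weight at least weekly in patients of 15 kg or less. Length has no counterpart.

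Two things are at stake. One is the validity of a safety variable in the youngest patients. The other is a grade that Section 17.6 ties to stopping treatment, in a trial that plans to randomise 10 patients, where one unneeded interruption is noticeable.

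**Working it through.** The plan states no figure on this point, so there is none to reproduce.

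**Inputs from the protocol.** GFR = KL/Pcr (Section 17.6). Table 4 absolute limits: grade 2 from below 90 to 60, grade 3 from below 60 to 30, grade 4 below 30. Table 4 falls from baseline: grade 2 from 10% to below 30%, grade 3 from 30% to below 50%, grade 4 from 50%.

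**Assumption.** g is proportional growth in length, shown from 2% to 30% because the documents give no growth rates.

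**Understatement.** With screening length L0 and current length L0(1+g), and the same K and Pcr, the ratio of screening-length to current-length eGFR is 1/(1+g). The understatement is 1 - 1/(1+g).

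**Absolute criterion.** The screening-length value drops below 60 when the current-length value is below 60(1+g), and below 30 when it is below 30(1+g). Values from 60 up to 60(1+g) are therefore graded 3 instead of 2, and values from 30 up to 30(1+g) are graded 4 instead of 3.

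**Percentage criterion.** Here g is growth since the baseline in use, because a fixed length cancels from the ratio. A true fall f reads as 1 - (1 - f)/(1+g), so the true fall that reads as 30% is 1 - 0.7(1+g).

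| g (assumed) | eGFR too low by | graded 3 instead of 2 | graded 4 instead of 3 | true fall that reads as 30% |
|---|---|---|---|---|
| 2% | 2.0% | 60 to 61.2 | 30 to 30.6 | 28.6% |
| 5% | 4.8% | 60 to 63 | 30 to 31.5 | 26.5% |
| 10% | 9.1% | 60 to 66 | 30 to 33 | 23.0% |
| 20% | 16.7% | 60 to 72 | 30 to 36 | 16.0% |
| 30% | 23.1% | 60 to 78 | 30 to 39 | 9.0% |

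**Growth alone, true function constant.** An apparent 10% fall (grade 2) needs g = 1/0.9 - 1 = 11.1%. An apparent 30% fall (grade 3) needs g = 1/0.7 - 1 = 42.9%.

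**One illustrative patient (all values assumed).** K = 0.45, Pcr = 0.50 mg/dl, length 60 cm at screening and 70 cm now, so g = 70/60 - 1 = 16.7%. Screening length gives 0.45 x 60/0.50 = 54, which is grade 3 on the absolute criterion. Current length gives 0.45 x 70/0.50 = 63, which is grade 2.

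**The case against.** The strongest reply is that the documents contain no rule to grade on an old length. Section 17.6 does not say which length enters later calculations, and nothing bars a fresh measurement. SAP Section 7.3.3 uses height as a baseline descriptor, which could explain why it is scheduled once. Section 17.6 also points to a study manual that is not available here. This stands as a limit on the claim: a reader might infer that children *are* graded on stale length, and the documents do not show that. They show a formula that needs length at each assessment and a schedule that supplies only the screening value. A site that follows the schedule has nothing else to enter, and sites that measure anyway will not be comparable with those that do not.

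The second reply is that the consequence is modest. The documents give no age distribution, and the grading tables also cover adults, so the number of infants is unknown. Table 4 allows Cockcroft-Gault where applicable. Grade 2 carries no stopping consequence there. A reader might also infer that growth by itself would force patients off drug. That is not supported: growth alone reaches the grade 3 percentage limit only at about 43%, the stop may be temporary, the synopsis says only *may*, and Section 17.6 leaves clinical significance to the investigator and asks that age be considered in grading. All of this stands. It reduces the size of the point but does not remove the bias in a planned safety variable.

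**Conclusion.** The point holds as a cheap improvement to a safety measure. It does not touch the definition of the primary endpoint, and study-drug dosing uses updated weight. Following the schedule as written biases eGFR low by 4.8% to 16.7% for assumed growth of 5% to 20%. The bias is toward over-grading near the limits. At 2% growth the misgraded band around 60 is about 1 unit, so the matter concerns infants and young children. The result rests on the assumed growth range and on sites using the only length the schedule provides.

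Two stronger readings are not supported.

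- **Dexamethasone dosed on stale height.** The course is set per m2, and "SOC tapering cycles may be used and can be repeated during the 18-week SAOL study period", but no method for body surface area is given. Section 9.1 speaks of the same glucocorticoid dosage in one place and the original dose in another. If the absolute dose is repeated, current height does not enter. If surface area were taken as the square root of length x weight/3600 (an assumption) with current weight and screening height, the understatement would be 1 - 1/sqrt(1+g): 2.4%, 4.7% and 8.7% at g = 5%, 10% and 20%, about half that for eGFR.
- **A change of K group hides a true decline.** K rises from 0.45 to 0.55 between groups (0.55/0.45 = 1.222), but this does not depend on when height is measured, and it partly offsets the length error. With a true 15% fall, the combined ratio is 0.85 x 1.222/(1+g), which is 0.99 at g = 5% and 0.90 at g = 15%. Neither is a rise.

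**What to change.** In Table 1 and Sections 13 and 14, schedule length or height together with weight at visits that include chemistry: at least V1 and V8, and periodically within each phase. In Section 17.6, state that L is the most recent measured value.

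The cost is a short measurement at visits that already record weight, and a wording change. At telemedicine visits it needs a home nurse or a local measurement.

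Two pairs of statements should be reconciled separately:

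- the synopsis (*may*) and Section 17.6 (*will*) on discontinuation after a grade 3 or 4 eGFR;
- the two descriptions in Section 9.1 of a repeat glucocorticoid course, so that it is clear whether the same mg/m2 or the same absolute dose is meant.

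Which reading is right in each pair is for the sponsor to decide. No grade limit, K rule or dose is proposed here.

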*** NOTE:**

Laboratory safety and efficacy endpoints will be studied at the visits by the central lab. For hospitalized patients local labs will perform, in addition, analyses as required by the standard of care and this information will be entered in the study eCRF.

14 CONDUCT OF THE STUDY

14.1 Schedule of Events

See section 7, [Table 1](#).

In order to protect the patient's and caregiver's safety and welfare during the COVID-19 pandemic, on-site study visits may not be considered appropriate; most patients have to travel to their study site and on-site study visits may expose both the patients and caregivers as well as study site personnel to an increased risk of infection. Moreover, due to the ultra-rare indication of this study, conducting on-site study visits at sites often located far away from the patient's home has made study conduct challenging.

Thus, in an effort to accommodate the patients and their families while ensuring the relevant study data is collected, scheduled study visits (except for the Baseline visit) may be conducted as telemedicine visits involving the use of electronic communications (for example, live interactive video and audio) to enable site staff to conduct "virtual" (not in-person) visits with their patients. These visits may be supported by home health nurses assisting in physical examination (by performing a body assessment supporting the physical examination done by the investigator via telemedicine), collection of vital signs or performance of central laboratory blood draws. Laboratory assessments may be also performed at qualified local laboratories. The study site may also utilize a physical examination from the patient's most recent standard of care visit conducted by the local treating physician, for the purpose of the study.

Patients and/or parents (or legal representative, if applicable) will sign a respective assent/informed consent prior to the conduct of such telemedicine visits.

It is expected that the Baseline Visit will be conducted as an on-site visit, as patients are having an active disease at that time and eligibility needs to be confirmed during an on-site visit. For the Screening visit, eligibility may be evaluated during a telemedicine visit. This visit shall be based on local laboratory results and standard of care physical examination, including vital signs, conducted by the local treating physician. This may be permitted in order to avoid long-distance travel for the patients with uncertainties whether they meet the protocol definitions for an active disease status.

For all visits after the Screening and Baseline visits, the risks and burden of travel to the study site versus the requirement for a close patient follow-up in line with protocol requirements will be evaluated for each individual patient. Aspects to consider include the disease severity of each patient, the distance from the patient's home to the study site, the patient's local situation of the COVID-19 pandemic and the possibilities and local regulatory requirements for telemedicine visits at the study sites.

SAOL Phase

